#### **9.7.3.5 Analysis of Other Information**

Descriptive statistics will be provided for alcohol/nicotine/drug/stimulant consumption.

Frequency tables with incidences and EAIR of AEs, SAEs, ADRs, and SADR will be provided on MedDRA SOC and PT level. The incidence and EAIR will be provided including 95% CIs. Listings of special situations (drug interactions, medication abuse, medication misuse, medication overdose, medication errors, unexpected therapeutic, or clinical benefit from product use, pregnancy or lactation exposure with the product, lack of efficacy, off-label use, and occupational exposure) will also be provided.

Further details will be specified in the SAP, which will be finalised before study database lock.

#### **9.7.4 Bias, Confounding and Effect-Modifying Factors**

The results in any observational study could be affected by potential bias and confounding. Potential selection bias with regards to the selection of patients being enrolled, the patients who consent to participate in the study or those who complete the study cannot be ruled out. To reduce selection bias, a consecutive enrolment of eligible patients is planned whenever possible.

In this study, careful attention should be paid to describe the patient population, and caution should be applied to the interpretation of results as there may be confounding factors, measured or unmeasured. Other potential biases may include differential or non-differential misclassification of exposure and outcome, as well as information bias due to missing information.

Possible confounding factors include site and baseline disease severity. These possible confounding factors will be addressed by means of stratification, if applicable. For more details see the SAP.

#### **9.7.5 Interim Analysis**

The first interim report is expected in Q3/Q4 2028. Further interim analyses will be provided every 2 years unless the final report is delivered until Q4 2030.

### **9.8 Quality Control**

#### **9.8.1 Data Quality**

A Steering Committee will review the study enrolment and make recommendations on the study's progress based on recruitment speed and characteristics of the patient population included to ensure that the study fulfils the pre-defined study objectives. These recommendations could relate to defining time points for interim analysis, assessing the need for any additional interim analyses, and providing insight into potential study amendments and adjustments of study related procedures, if necessary, in order to achieve the study goals. These recommendations would be presented in the progress or interim reports, as appropriate. The Steering Committee is also responsible for overseeing possible publications from the study.

Before starting the PASS, the sites will be trained on the background and objectives of this study and on ethical as well as regulatory obligations. Training and discussion on the usage of the EDC system and completion of the eCRF will be provided.

A CRO will be selected and assigned for EDC system development, quality control, verification of the data collection, data analysis and data transfer to the MAH.

All outcome variables and covariates will be recorded in a standardised eCRF. After data entry, missing or implausible data will be queried and the data will be validated. A check for multiple documented patients will be done. Information from the RMP targeted follow-up questionnaires will be examined and utilised, as appropriate (further information to be provided in the DMP).

Detailed information on checks for completeness, accuracy, plausibility, and validity are given in the DMP. The same plan will specify measures for handling of missing data and permissible clarifications. The DMP is available upon request (see section 15.1).

National and international data protection laws as well as regulations on observational studies will be followed.

### **9.8.2 Monitoring**

Quality review will be done in two steps: in the first step the site's training status will be assessed via standardised telephone interviews. In the second step, source data verification (SDV) will be conducted in approximately 20% of sites by on-site visits. The monitoring process will be defined in the monitoring plan. The purpose is to review the documented data for completeness and plausibility, adherence to the study protocol and verification with source documents. The documents must be available for review in the event the site is selected for monitoring, audits, or inspections. The monitoring plan is kept as a stand-alone document and listed in section 15.1.

### **9.8.3 Storage of Records and Archiving**

The marketing authorisation holder (MAH) will make sure that all relevant documents of this PASS including eCRFs and other patient records will be stored after end or discontinuation of the study at least for 25 years. Other instructions for storage of medical records will remain unaffected.

The physicians participating in the study have to archive documents at their sites according to local requirements, considering possible audits and inspections from the MAH and/or local authorities. It is recommended to also store documents for a retention period of at least 10 years. The documents must be available for review in the event the site is selected for monitoring, audits, or inspections and must be safely archived.

## **9.9 Limitations of the Research Methods**

Possible limitations of the study are based on the observational design and the fact of voluntary participation of physicians and patients. Physicians and patients who voluntarily agree to participate in this study might differ from those who do not agree. Consecutive enrolment should avoid any selection bias and increase the likelihood of representativeness.

Although the study aims to include participants from a variety of geographic regions, there may be local limitations that reduce the representativeness of patients recruited, such as

patient access to recruiting physicians (including differences in patient profile in specialized, recruiting sites vs local general practice), Yselty® availability and reimbursement, and decisions relating to local standard of care.

The main objective depends on two factors that are crucial but beyond the control of the study: First, the overall uptake of Yselty® and the proportion of patients treated beyond 12 months. Second, the extent to which doctors perform DXA scans after 1 year (as recommended in the SmPC) as part of their routine care. Depending on the country, this could be either facilitated or hindered by the reimbursement status of DXA scans.

BMD measurements, the primary objective, have a good reproducibility under highly controlled conditions, but such conditions do not generally apply in clinical practice. Many factors could affect the accuracy of BMD testing, including inter-machine variance as well as the experience of the operator. In addition, a high rate of missing BMD measurements at week 24 and week 52 due to study discontinuations was observed in the two pivotal studies [11]. This indicates that BMD assessment may become difficult due to the low number of observations recorded, especially for long-term users which are of special interest in this study. When interpreting the proportion of patients with z-scores below -2 standard deviations indicating loss of bone density, it should be kept in consideration that normalisation of z-scores is usually based on BMD measurements for a single bone. If multiple measurements have been taken in a patient, the likelihood of results being below threshold increases with the number of bone sites examined for each patient.

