### 9.1.2 Endpoints

The primary endpoint of objective **I**. is only assessed in patients with long-term treatment (>12 months) and is:

- Number and proportion of patients with a lumbar spine, total hip, or femoral neck BMD z-score below the threshold of -2 standard deviations.

The exploratory endpoints of this study are:

- For objective **II.a**:
  - Incidence rate of osteoporosis or fractures suspected to be due to osteoporosis; all suspected osteoporotic fractures (minimal- or non-traumatic) of long bones or spine where the physicians suspect an osteoporotic cause of the fracture
- For objective **II.b**:
  - Number and proportion of patients with elevated liver enzyme levels above the upper limit of normal
  - Incidence rate of adverse events suggestive of liver injury or related to liver enzyme elevation
- For objective **II.c**:
  - Incidence rate of adverse events regarding mood disorders including mood swings, affect lability, emotional disorder, irritability, mood altered, anxiety, bipolar disorder, mania, depression, depressed mood
- For objective **II.d**:
  - Incidence rate of uterine endometrial adenocarcinoma events
  - Incidence rate of mammary gland adenocarcinoma events

---

Additional analyses on ADRs will be performed.

 The RMP (see section 15.1) contains targeted follow-up questionnaires for these events. Physicians who report these events will be asked to fill the corresponding targeted follow-up questionnaire.

 The RMP (see section 15.1) contains targeted follow-up questionnaires for these events. Physicians who report these events will be asked to fill the corresponding targeted follow-up questionnaire.

 A list of MedDRA terms for hepatic events is available as a stand-alone document (see section 15.1).

- For objective **II.e**:
  - Number and proportion of patients starting each Yselyt® dosing regimen, time spent on each dosing regimen, and changes in dosing regimens
- For objective **II.f**:
  - Patient adherence to prescribed treatment, including ABT
- For objective **II.g**:
  - Incidence rate of adverse events for cardiac disorders (ventricular arrhythmias [e.g., ventricular tachycardia and ventricular fibrillation, flutter, torsade de points], cardiac arrest, and sudden cardiac death) suggestive of potential QT interval prolongation

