### **9.5 Study Size**

Approximately 1,000 women of reproductive age with documented uterine fibroids and symptoms such as HMB being treated with Yselyt® long-term, according to the SmPC. This is a multinational study in 5 European countries (Germany, Italy, Spain, Poland and UK), whereas the selection and sequence of countries may change depending on the launch dates of Yselyt®. The number of study sites will vary per country, dependent on use of Yselyt®.

This is a descriptive study and is not intended to test a formal hypothesis. The sample size is based on feasibility and practical considerations rather than statistical. Sample size considerations are based on the primary endpoint, BMD z-score, which compares bone mineral density with a reference population of the same age and sex. The BMD z-score will

---

 Special situations include drug interactions, medication abuse, medication misuse, medication overdose, medication errors, unexpected therapeutic or clinical benefit from product use, pregnancy or lactation exposure with the product, lack of efficacy, off-label use, and occupational exposure (see section 11.4).

be measured at 3 sites for each patient, i.e., lumbar spine, total hip, and femoral neck and the lowest individual value is used to estimate the population proportion.

A single-group design was used to obtain a 2-sided 95% confidence interval (CI) for a single proportion. Given the standard normal distribution of BMD z-scores (z-distribution), the expected sample proportion of values < -2 (cutoff for low bone density) is assumed to be 2.5%, which corresponds to the lower 2.5% quantile of the z-distribution. With an effective sample size of 800 (assuming 20% dropout), the CI width at 12 months of follow-up is 2.2% and the expected precision of the proportion is 2.5%±1.1% (see Table 2). Assuming a further 20% yearly dropout rate, at 24 months of follow-up, the effective sample size is estimated to be 640 patients with a CI width of 2.4% and an expected precision of the proportion of 2.5%±1.2%. At 36 months of follow-up, the effective sample size is estimated to be 512 patients with a CI width of 2.8% and an expected precision of the proportion of 2.5%±1.4%. At 48 months of follow-up, the effective sample size is estimated to be 409 patients with a CI width of 3.0% and an expected precision of the proportion of 2.5%±1.5%.

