#### **9.7.3.3 Analysis of Primary Endpoint**

The primary objective will only be assessed in users with the long-term treatment (>12 months) and where z-scores of lumbar spine, total hip, or femoral neck are available. For rates of events of BMD z-scores below the age-related threshold of -2 standard deviations, the number and percentage of patients with these events will be provided including 95% CIs.

The aggregated number, frequency of DXA scans, anatomic site of DXA scan, machine type, and imaging parameters of DXA scans during the observational period will be analysed by descriptive statistics. If results of DXA scans can be interpreted in a categorised way, shift tables for the change from baseline, will be provided, where available. If images of the DXA scans can be provided by the doctors, they will be reviewed by 1 independent expert for their suitability and included in an additional sensitivity analysis.

Sensitivity analyses using different criteria (e.g., machine type) to select DXA scans that ensure their comparability will be performed to evaluate the primary endpoint if the sample size allows (e.g., if more than 30 patients remain after selection of suitable cases) and will be further detailed in the SAP.

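### The primary proportion below a z-score of -2 is a prevalence of low bone density for age, but Section 9.9 reads it as loss, and the primary count does not separate women already below -2 before Yselty

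*Protocol*

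**What the plan says.** Protocol Section 9.1.2 restricts the primary endpoint to treatment beyond 12 months and defines it as "Number and proportion of patients with a lumbar spine, total hip, or femoral neck BMD z-score below the threshold of -2 standard deviations". Section 9.7.3.3 limits the analysis to long-term users who have a z-score from at least one of the three sites: "The primary objective will only be assessed in users with the long-term treatment (>12 months) and where z-scores of lumbar spine, total hip, or femoral". It then states the output: "For rates of events of BMD z-scores below the age-related threshold of -2 standard deviations, the number and percentage of patients with these events", with 95% confidence intervals. Neither section requires an earlier scan or sets aside women who were below -2 before treatment.

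Section 9.5 explains the z-score as a measure "which compares bone mineral density with a reference population of the same age and sex". The planning value follows from that. Its premise is worded "Given the standard normal distribution of BMD z-scores (z-distribution"; the figure drawn from this premise is given as "the expected sample proportion of values < -2 (cutoff for low bone density) is assumed to be 2.5"%.

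Section 9.9 gives the same quantity another meaning: "the proportion of patients with z-scores below -2 standard deviations indicating loss of bone density".

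Change within a woman is addressed in two other places. Section 9.7.3.3 says that, if DXA results can be put into categories, "shift tables for the change from baseline, will be provided, where available". Exploratory objective II.j (Sections 8, 9.1.2 and 9.7.3.4) summarises change in density, z-score and t-score from baseline or from the 12-month scan. Section 9.1.2 notes that a baseline scan is recommended only for women at high risk.

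**The concern.** A z-score below -2 on treatment says where a woman stands against her age peers at that scan. It does not say that she moved. A woman at -2.2 before treatment and -2.2 at month 24 is counted; a woman who falls from +1.0 to -1.5 is not. Section 9.5 is consistent with this: its 2.5% is the lower tail of a reference population and contains no drug effect. Section 9.9 is not, because it takes the same proportion to show loss.

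The background in Section 7 is concerned with sustained BMD loss over time. A primary figure that mixes existing with new low density is a blunt measure of that. Section 9.1 also plans to set the BMD results of women on add-back therapy from the start beside published data for another product. Differences in starting density could then be taken for differences in loss.

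**Working it through.** **Inputs from the protocol.** Expected proportion 2.5%, standard normal z-scores, two-sided 95% interval, 1,000 women with 20% yearly dropout (Section 9.5 and Table 2).

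**The plan's own figures.** The half-width is 1.96 × √(p(1 − p)/n) with p = 0.025.

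| n | Half-width computed | Table 2 |
|---|---|---|
| 800 | 1.08% | 1.10% |
| 640 | 1.21% | 1.20% |
| 512 | 1.35% | 1.35% |
| 409 | 1.51% | 1.50% |

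At n = 800 the interval is 0.0142 to 0.0358, against 0.014 to 0.036 in the table. The planning figures reproduce, and they are figures for no drug effect.

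**Expected count with no drug effect.** 0.025 × 800 = 20. The exact tail is Φ(−2) = 2.275%, and 0.02275 × 800 = 18.2. So about 18 to 20 women are expected below -2 if all 800 are scanned.

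**How many were below -2 beforehand, with no drug effect.** If z-scores were perfectly stable, all of them. With test-retest correlation r, the share is P(Z₁ < −2 and Z₂ < −2)/Φ(−2) under a bivariate normal. The protocol gives no r, so these values are assumptions.

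| r | Already below, of 800 | New by noise, of 800 | Share already below |
|---|---|---|---|
| 1 | 18.2 | 0 | 100% |
| 0.99 | 15.8 | 2.4 | 87% |
| 0.95 | 12.8 | 5.4 | 70% |
| 0.90 | 10.7 | 7.5 | 59% |

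**How many were below -2 beforehand, with a drug effect.** Suppose every z-score falls by d, at one site and without noise. The follow-up proportion is Φ(−2 + d) and the share already below is Φ(−2)/Φ(−2 + d). The values of d are assumptions.

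| d (SD) | Proportion below -2 | Count of 800 | Already below | Share already below |
|---|---|---|---|---|
| 0.1 | 2.87% | 23.0 | 18.2 | 79% |
| 0.2 | 3.59% | 28.7 | 18.2 | 63% |
| 0.3 | 4.46% | 35.7 | 18.2 | 51% |

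**Single site against lowest of three.** Section 9.5 uses the lowest of three sites. With no drug effect and assumed inter-site correlations from 0.9 to 0.5, the expected proportion is 3.8% to 5.8% (31 to 46 of 800). Section 9.9 already warns of this effect. It does not mention density that was low before treatment.

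**The case against.** The strongest reply is that the protocol already studies change. Objective II.j reports within-patient change from baseline or from the 12-month scan, so the woman who falls from +1.0 to -1.5 appears there. A shift table cut at -2 would show who was already below and who is new. A reader might infer that the plan has no measure of loss; it has. What remains is that II.j gives mean changes, the shift tables are conditional and run only from baseline, and neither divides the primary count.

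A reader might also infer that every counted woman is a false loss when the drug has no effect. That needs perfectly stable z-scores, and Section 9.9 itself describes machine and operator variation. Nor can the share already below be fixed from the document: Section 9.2.3 excludes SmPC contraindications, whose content is not given and which may remove some women with known low density.

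The word *events* in Section 9.7.3.3 might be taken to claim new onset. It does not carry that weight. Section 9.1.2 keeps incidence-rate language for other endpoints and states this one as a number and proportion.

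Finally, the phrase in Section 9.9 is a subordinate clause in a sentence that urges caution. It is not a reporting rule, the study tests no hypothesis, and no section attributes the primary proportion to treatment. So the protocol does not commit the report to a finding of drug-induced loss. The clause still gives a reading of the primary figure that Section 9.5 contradicts.

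**Conclusion.** The point holds as an inconsistency about what the primary number means, together with a missing split of that number. The endpoint is the prevalence of low BMD for age in long-term users. The planning value is what the reference population would show with no drug effect, about 18 to 20 of 800 at a single site. Reading it as loss is unsupported.

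Under the assumed correlations and shifts, between half and nearly nine tenths of the counted women would have been below -2 before treatment. Those shares rest on normal z-scores, one site, all 800 women scanned and inputs that the protocol does not give. They show the order of size and are not predictions. The primary proportion remains computable and worth reporting; the correction concerns its label and its breakdown.

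**What to change.** In Section 9.9, replace the reference to loss with *indicating low bone density for age*, in line with Section 9.5.

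In Section 9.7.3.3, label the overall proportion as prevalence of low BMD for age and split its numerator into three:

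- already below -2 at the pre-treatment scan;
- newly below -2 since the pre-treatment scan;
- no pre-treatment scan.

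Give the newly-below proportion with a 95% interval among women at or above -2 at the pre-treatment scan. Report crossings after the 12-month scan separately, and state that they miss women who crossed in the first year. Do not pool the two references: pre-treatment scans come mainly from high-risk women, and the 12-month scan is already on treatment. Apply the comparability conditions of Section 9.7.3.4 (machine type, scan location, at least 6 months between scans). Base any statement about loss on II.j and these within-patient figures.

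The cost is wording in two sections and one extra table from scans and dates already collected. The newly-below figures will rest on fewer women, mainly high-risk women for the pre-treatment reference, and will have wider intervals. They will also include some crossings by measurement noise: about 2 to 8 per 800 with no drug effect at the correlations assumed above.

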### **9.10 Other Aspects**

Not applicable.

## **10 Protection of Human Subjects**

### **10.1 Ethical Conduct of the Study**

This study is a non-interventional PASS. Yselty® is prescribed in the usual manner in accordance with the SmPC under the sole decision of the treating physician. The treatment decision falls within current established practice. No additional diagnostic, therapeutic or monitoring processes are required for participation or during the study and the prescription of the medicine is clearly separated from the decision to include the patient in the study. Epidemiological methods will be used for the analysis of the collected data.

### **10.2 Regulatory Authorities Approvals/Authorisations**

The study will be carried out within an approved indication in accordance with guidelines and regulations of EMA, and applicable local law(s) and regulation(s) (e.g., Regulation (EU) No 520/2012 [12]). Recommendations given by other organisations will be followed as well (e.g., EFPIA [13], ENCePP [14]). ICH-GCP guidelines will be followed whenever possible.

In addition, the guidelines on Good Pharmacovigilance Practices (GVP [15, 16]) will be followed; the relevant competent authorities of the EU member states will be notified according to Volume 9A [16].

### **10.3 Independent Ethics Committee/Institutional Review Board**

In all countries where reference to an Independent Ethics Committee (IEC) is required, documented approval from appropriate IECs will be obtained for all participating centres prior to study start. When necessary, an extension, amendment or renewal of the IEC approval must be obtained and forwarded to the MAH. The IEC must supply to the MAH, upon request, a list of the IEC members involved in the vote and a statement to confirm that the IEC is organised and operates according to applicable laws and regulations.

